8. STUDY ASSESSMENTS AND PROCEDURES

8.1. Administrative and General Procedures

Participants transitioning into the extension period of the study will have efficacy and safety assessments performed in accordance with the standard of care at each investigational site for the participant's condition and monitoring at the investigator's discretion and not less than every 8 to 12 weeks (see Table 2). Unless noted below, procedures listed in this section are not required to be performed in the extension period of the study.

8.1.1. Administration of Informed Consent Form

Valid informed consent must be obtained from the study participant before conducting any study-specific procedures using an ICF approved by the local IRB/IEC that contains all elements required by ICH E6, and describes the nature, scope, and possible consequences of the study in a form understandable to the study participant. Local and institutional guidelines for ICF content and administration must be followed; the original signed ICF must be retained by the investigator, and a copy of the signed ICF must be provided to the study participant. The informed consent process for each participant must be documented in writing within the source documentation.

8.1.2. Screening Procedures

Screening is the interval between the signing of the ICF and the day that the participant is administrated the first dose of study drug (Day 1). Informed consent must be obtained before performing any study specific procedures. Assessments that are required to demonstrate eligibility may be performed over the course of 1 or more days during the screening process.

All information associated with eligibility requirements must be entered into the appropriate eCRF pages.

Results from the screening visit evaluations will be reviewed to confirm eligibility before enrollment or the administration of study drug. Tests with results that fail eligibility requirements may be repeated during screening if the investigator believes the results to be in error. For screening assessments that are repeated, the most recent available result before treatment will be used to determine eligibility and entered into the eCRF. Treatment should start as soon as possible. Additionally, a participant who fails screening may repeat the screening process if the investigator believes there has been a change in eligibility status (eg, after recovery from an infection).

8.1.3. Interactive Response Technology Procedure

Each participant will be identified in the study by a participant ID number, which is a combination of the site ID and participant number. Site staff should contact IRT to obtain the participant ID number during screening. IRT will be contacted at each regular study visit to update the study drug supply. Additional details are provided in the IRT Manual.

8.1.4. Demography and Medical History

8.1.4.1. Demographics and General Medical History

Demographic data and general medical history will be collected at screening.

8.1.4.2. Disease Characteristics and Treatment History

A disease-targeted medical and medication history, including date of diagnosis of AIHA, serological test, rituximab treatment history and other details related to the disease under study, will be collected at screening.

8.1.5. Prior and Concomitant Medications and Procedures

Prior and concomitant medications and procedures will be reviewed to determine participant eligibility. All concomitant medications and measures must be recorded in the eCRF, and any medication received or procedure performed within screening period before enrollment and up to the end of the follow-up period (see Table 1) will be recorded in the eCRF. The medication record will be maintained after signing the ICF to document concomitant medications, including any changes to the dose or regimen. Concomitant medications include any prescription, overthe-counter, or natural/herbal preparations taken or administered during the study period. Concomitant treatments and/or procedures that are required to manage a participant's medical condition during the study will also be recorded in the eCRF.

Extension Period

Use of concomitant medications should be monitored as described in Table 2 for participants in the extension period of the study to verify that participants are not taking any concomitant medication prohibited per Section 6.7.3.

8.2. Efficacy Assessments

Efficacy assessments are conducted at the visits noted in Table 1.

8.2.1. Hemoglobin Level, Hemolysis Markers, Direct Antiglobulin Test, and Complement Assessment

Participants will undergo hematology, serum chemistries, hemolysis markers, DAT, and complement assessment (CH50, C3, and C4) to evaluate type of AIHA diagnosis and disease status (see Table 5).

Note: For the purpose of participants' enrollment eligibility and safety and efficacy assessments, blood samples for hematology panels, including CBC and differential count, will sent to a local laboratory for analysis (see Table 5). All other Protocol-required blood samples aside from hematology panels will be sent to the central laboratory for analysis. Local laboratory

hematology panel results and central laboratory results for all other assessments will be entered into the eCRF.

8.2.2. Direct Antiglobulin Test and Cold Agglutinin Test

Direct antiglobulin tests for the detection of IgG and complement bound to RBCs will be performed at a central laboratory or local laboratory at screening visit (see Table 1 and Section 5.1). If DAT was performed within 28 days before screening at the study site, the participant does not need to retest DAT at the screening visit. However, if DAT was performed greater than 28 days before screening or performed in a location other than the study site, the sponsor will review and make a recommendation if retesting DAT is required.

8.3. Safety Assessments

Safety assessments are conducted at the visits noted in Table 1 and Table 2.

Extension Period

Adverse events leading to treatment discontinuation, all AEs suspected to be TEAEs and all SAEs regardless of causality relationship will be reported on the AE eCRF during the extension period.

8.3.1. Adverse Events

Adverse events will be monitored from the time the participant signs the ICF. Participants will be instructed to report all AEs during the study and will be assessed for the occurrence of AEs throughout the study. In order to avoid bias in eliciting AEs, participants will be asked general, nonleading questions such as "How are you feeling?" All AEs (serious and nonserious) must be recorded on the source documents and eCRFs regardless of the assumption of a causal relationship with the study drug. The definition, reporting, and recording requirements for AEs are described in Section 9.

8.3.2. Physical Examinations

Abnormalities that are considered clinical significant in the judgment of the investigator are to be reported as AEs.

Physical examinations must be performed by a medically qualified individual such as a licensed physician, physician's assistant, or an advanced registered nurse practitioner, as local law permits.

8.3.2.1. Comprehensive Physical Examination

At screening, Day 1, and EOS, a comprehensive physical examination should be conducted. The comprehensive physical examination will include assessment(s) of the following organ or body

systems: skin; head, eyes, ears, nose, and throat; thyroid; lungs; cardiovascular system; abdomen (liver, spleen); extremities; and lymph nodes; as well as a brief neurological examination. Height and body weight will be assessed only at the Day 1 visit.

8.3.2.2. Targeted Physical Examination

At all other study visits except at screening, Day 1, and EOS, the targeted physical examination will be a symptom-directed evaluation. The targeted physical examination will include assessment(s) of the body systems or organs, as indicated by participant symptoms, AEs, or other findings.

8.3.3. Vital Signs

Vital sign measurements include blood pressure, pulse, respiratory rate, and body temperature. Blood pressure and pulse will be taken with the participant in the recumbent, semirecumbent, or sitting position after 5 minutes of rest. Clinically notable abnormalities that are considered clinically significant in the judgment of the investigator are to be reported as AEs.

8.3.4. Electrocardiograms

All 12-lead ECGs will be performed with the participant in a recumbent or semirecumbent position after 5 minutes of rest. The 12-lead ECGs will be performed locally and be interpreted by the investigator at the site and used for immediate participant management. Interpretation of the 12-lead ECG will be used to determine eligibility at screening. An additional ECG will be performed at Week 2, Week 8, and the EOT visit (Week 12) or earlier, if the participant discontinues treatment). Throughout the study, a 12-lead ECG may be conducted if associated with an AE or other signs or symptoms. The decision to include or exclude a participant or discontinue his or her participation in the study based on an ECG flagged as "Abnormal, Clinically Significant" is the responsibility of the investigator, in consultation with the sponsor's medical monitor, as appropriate. Clinically notable abnormalities that are considered clinically significant in the judgment of the investigator are to be reported as AEs.

8.3.5. Laboratory Assessments

Blood draws for laboratory assessments will occur at study visits indicated in the schedule of assessments (see Table 1). Specific laboratory assessments are provided in Table 5. Blood may be drawn in pediatric tubes to minimize blood loss from phlebotomy.

All laboratory assessments will be performed at a central laboratory, with the exception of the following, in which case the investigative site laboratory or an accredited local laboratory may be used:

- Hematology panels (see Table 5), including CBC and differential count, will be sent to a local laboratory for analysis (see Section 8.2.1).
- For local laboratory assessments deemed necessary by the investigator for participant management (ie, dose modification, SAE, or COVID-19 restrictions affecting travel to the site for extension visits). Note: Such assessment data and reference ranges must be recorded in the participant's eCRF.

Extension Period:

Laboratory assessments (see Table 5) including hematology panels and hemolysis markers need to be performed in accordance with standard of care at each investigational site for the participant's condition and monitoring at the investigator's discretion and not less than every 8 to 12 weeks. Any other clinical lab monitoring should be done per the investigator's judgment for monitoring any other clinical conditions. Laboratory results will need to be documented in the eCRF.

8.3.5.1. Chemistry and Hematology

All chemistry assessments (see Table 1 and Table 5) will be performed from blood samples collected using institutional best practices (refer to the Laboratory Manual). Hematology panels will be analyzed by local laboratories.

8.3.5.2. Vitamin B12 and Folic Acid

Vitamin B12 and folic acid will be tested at screening. Participants who are deficient in either folic acid or vitamin B12 will have replacement determined by the investigator as per standard of care.

8.3.5.3. Iron Clinical Assessment

All participants will have iron assessments (iron, total iron-binding capacity, ferritin) at screening. If elevated ferritin levels are present (> 200 ng/mL in women or > 250 ng/mL in men), additional testing and follow-up recommendations will be provided to the investigator in consultation with the medical monitor. These recommendations will include evaluation of the liver (serum transaminases and MRI) and for other causes of iron overload as indicated by the participant's medical history.

Iron assessments will be repeated during the study at Week 6 if the participant has ongoing transfusion requirements during the study.

8.3.5.4. Urinalysis

Urinalysis will be performed by a central laboratory at screening and EOT or if the participant discontinues treatment (see Table 1 and Table 5).

8.3.5.5. Coagulation

A D-dimer assessment (see Table 5) will be performed from blood samples collected using institutional best practices (refer to the Laboratory Manual).

8.3.5.6. Pregnancy Testing

A serum pregnancy test will be required for all women of childbearing potential during screening. Urine pregnancy tests will be conducted as outlined in Table 1, as medically indicated, or per country-specific requirement. Urine pregnancy tests will be done locally. If a urine pregnancy test is positive, the results should be confirmed with a serum pregnancy test, which may be performed locally.

If the serum pregnancy test is negative after a urine test was positive, the investigator will assess the potential benefit/risk to the participant and determine whether it is in the participant's best interest to resume study drug and continue participation in the study.

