Table 1: Schedule of Assessments

		Screening				Trea	tment					Follow-Up ^a	ı
Procedure	Protocol Section		Day 1	Wk 1 ± 3 days	Wk 2 ± 3 days	Wk 4 ± 3 days	Wk 6 ^b ± 3 days	Wk 8 ± 3 days	Wk 10 ± 3 days	Wk 12 ± 3 days (EOT)	Month 1 + 5 days	Month 2 ± 5 days	Month 3 ± 5 days (EOS)
Administrative procedures													
Informed consent	8.1.1	X											
Contact IRT	8.1.3	X	X	X	X	X	X	X	X	X	X	X	X
Review inclusion and exclusion criteria	5.1, 5.2	X	X										
Demography and medical history	8.1.4	X											
Prior/concomitant medications	8.1.5	X	X	X	X	X	X	X	X	X	X	X	X
Study drug accountability and assess compliance	6.5			X	X	X	X	X	X	X			
Study drug dispensing	6.1		X			X		X					
Prophylactic treatment for PJP	6.7.1.1		X	X	X	X	X	X	X	X	X	X	X
Safety procedures/assessments													
Physical examination ^c	8.3.2	Xc	X ^{c,d}	X	X	X		X		X			Xc
Vital signs ^e	8.3.3	X	X	X	X	X	X	X	X	X			X
Serology ^f	8.3.5.7	X											
D-Dimer	8.3.5.5	X				X		X		X			
Vitamin B12/folic acid	8.3.5.2	X											
FSHg	8.3.5.6	X											
Serum pregnancyh	8.3.5.6	X											
Urine pregnancy ^h	8.3.5.6		X	X	X	X	X	X	X	X			
Urinalysis	8.3.5.4	X								X			
Serum chemistries ⁱ	8.3.5.1 8.3.5.3	X	X	X	X	X	X	X	X	X	X	X	X
12-Lead ECG ^j	8.3.4	X			X			X		X			
AE assessment	8.3.1	X	X	X	X	X	X	X	X	X	X	X	X

Table 1: Schedule of Assessments (Continued)

		Screening	Treatment							Follow-Up ^a			
Procedure	Protocol Section	Days -28 to -1	Day 1	Wk 1 ± 3 days	Wk 2 ± 3 days	Wk 4 ± 3 days	Wk 6 ^b ± 3 days	Wk 8 ± 3 days	Wk 10 ± 3 days	Wk 12 ± 3 days (EOT)	Month 1 + 5 days	Month 2 ± 5 days	Month 3 ± 5 days (EOS)
Efficacy assessments													
Hematology	8.2.1	X	X	X	X	X	X	X	X	X	X	X	X
Hemolysis markers ^k	8.2.1	X	X	X	X	X	X	X	X	X	Xk	X^k	Xk
DAT and cold agglutinin levels	8.2.2	X								X			
Complement assessment (CH50, C3, and C4)	8.2.1		X							X			
FACIT-Fatigue sub-scale	8.2.3		X				X			X	X	X	X
PK plasma sampling ^l	8.4			X	Xm			Xm		X			

^m No food intake 4 hours predose and 1 hour postdose on Weeks 2 and 8.

VV-CLIN-000602 CONFIDENTIAL

^a For participants who are not eligible to enter into the extension period.

^b Dose modification.

^c Comprehensive physical examination at screening, Day 1, and EOS; targeted physical examination at all other time points.

^d Height and body weight will only be assessed at Day 1.

^e Vital signs will include body temperature, respiratory rate, blood pressure, and pulse.

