f Serology includes HIV, hepatitis, anti-Streptolysin antibody, and anti-phospholipid antibody tests.

g For women of nonchildbearing potential only (ie, surgically sterile with a hysterectomy and/or bilateral oophorectomy OR postmenopausal, defined by last menstrual period > 12 months before screening and confirmed by FSH).

^h For women of childbearing potential only.

¹ Ferritin, iron, and total iron-binding capacity will be tested at screening for all participants and at Week 6 if the participant has ongoing transfusions requirements during the study.

Single ECG. At screening, in the event that a single QTcF is > 470 milliseconds for males or > 480 milliseconds for females, triplicate ECG measurements may be performed.

k Hemoglobin, haptoglobin, LDH, reticulocyte count, total bilirubin and direct/indirect bilirubin are hemolytic markers will be measured. During follow-up, these hemolytic markers should be assessed if a participant becomes symptomatic or starts new treatment; relevant biomarkers should also be included.

Plasma for PK analysis will be collected predose and 1, 2, and 4 hours postdose at Weeks 2 and 8. Predose PK will be collected at Weeks 1 and 12.

Table 2: Schedule of Assessments for the Extension Period

		Extension Period			Follow-Up	
Procedure	Protocol Section	At Least Every 8-12 Weeks in Clinic	EOT Extension Period	Month 1 + 5 days	Month 2 ± 5 days	Month 3 ± 5 days (EOS)
Prior/concomitant medications	8.1.5	X	X	X	X	X
Study drug dispensing	6.1	X				
Study drug accountability and assess compliance	6.5	X	X			
AE assessment	8.3.1	X	X	X	X	X
Prophylactic treatment for PJP	6.7.1.1	X	X	X	X	X
Hematology ^{a,b}	8.2.1	X	X	X	X	X
Hemolysis markers ^a	8.2.1	X	X	X	X	X
Serum chemistries ^a	8.3.5.1	X				

^a Performed at each site as per the standard of care for participant's condition and monitoring at the investigator's discretion. Frequency to be determined by the investigator if it is necessary to monitor any other ongoing clinical condition.

^b Hematology panel will be performed at local laboratory.

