An internal Safety Review Committee (see Section 9.6) will review clinical response and AE data. If there is no clinical response (CR or PR) by Week 12 in the first cohort of 10 participants, including those who receive dose escalation to 2.5 mg, the study will be stopped for futility. If there is a clear emerging signal from either Cohort 1 or Cohort 2, the committee may make recommendations as to the expanded study of either cohort to obtain additional safety and efficacy data at either dose level.

Participants who complete the 12-week treatment period and demonstrate clinical benefit from study drug may enter into an extension period with sponsor approval to continue receiving INCB050465 until the drug is available through another clinical study, or is commercially available, or the sponsor stops the study or the study drug development. Visits during the extension period will be conducted every 8 to 12 weeks to continue to monitor the effectiveness of the clinical response, as well as clinical safety laboratory assessments and adverse events.

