5.1. Inclusion Criteria

A participant who meets all of the following criteria may be included in the study:

- 1. Men or women, aged 18 years or older.
- 2. Diagnosis of AIHA based on the presence of hemolytic anemia and serological evidence of anti-erythrocyte antibodies, detectable by the DAT as follows:
 - a. Warm: DAT positive for IgG only or IgG plus C3d
 - b. Cold (CAD): DAT positive for C3d only, with cold agglutinins of I specificity
 - c. Mixed: DAT positive for IgG and C3d, with coexistence of warm autoantibodies and high titer cold agglutinins
- 3. Participants who have disease progression after treatment with standard therapies that are known to confer clinical benefit or who are intolerant to treatment. There is no limit to the number of prior treatment regimens.
- 4. Hemoglobin 7 to 10 g/dL (as determined by local laboratory).
- 5. No evidence of a lymphoproliferative malignancy or other autoimmune-related underlying conditions (eg, systemic lupus erythematosus, Castleman's disease, Sjögren's syndrome, or other autoimmune diseases).

- 6. ECOG performance status score of 0 to 2 (see Appendix C and Oken et al 1982).
- 7. Willingness to avoid pregnancy or fathering children based on the criteria below:
 - a. Woman of nonchildbearing potential (ie, surgically sterile with a hysterectomy and/or bilateral oophorectomy OR postmenopausal, defined by last menstrual period > 12 months before screening and confirmed by FSH).
 - b. Woman of childbearing potential who has a negative serum pregnancy test at screening and who agrees to take appropriate precautions to avoid pregnancy (with at least 99% certainty) from screening through at least 93 days after the last dose of study drug. Permitted methods that are at least 99% effective in preventing pregnancy (see Appendix A) should be communicated to the participant and her understanding confirmed.
 - c. Man who agrees to take appropriate precautions to avoid fathering children (with at least 99% certainty) from screening through at least 93 days after the last dose of study drug. Permitted methods that are at least 99% effective in preventing pregnancy (see Appendix A) should be communicated to the participant and his understanding confirmed.
- 8. Able to comprehend and willing to sign an ICF.
- 9. Willingness to receive PJP prophylaxis during the study period.

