7.1.1. Permanent Discontinuation of Study Treatment

Participants **must** be withdrawn from study drug for the following reasons:

- The participant becomes pregnant.
- Consent is withdrawn.

Note: Consent withdrawn means that the participant can no longer be followed. Participants may choose to discontinue study drug and remain in the study to be followed.

- Further participation would be injurious to the participant's health or well-being, in the investigator's medical judgment.
- The study is terminated by the sponsor.
- The study is terminated by the local health authority, IRB, or IEC.

A participant **may** be discontinued from study drug as follows:

- If, during the course of the study, a participant is found not to have met eligibility criteria, the medical monitor, in collaboration with the investigator, will determine whether the participant should be withdrawn from the study.
- If a participant is noncompliant with study procedures or study drug administration in the investigator's opinion, the sponsor should be consulted for instruction on handling the participant.

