9.4. Pregnancy

Pregnancy, in and of itself, is not regarded as an AE unless there is suspicion that study drug may have interfered with the effectiveness of a contraceptive medication or method. When a pregnancy has been confirmed in a participant during maternal or paternal exposure to study drug, the following procedures should be followed in order to ensure participant safety:

- The study drug must be discontinued immediately.
- The investigator must complete and submit the Incyte Clinical Trial Pregnancy form to the sponsor or its designee within **24 hours** of learning of the pregnancy.

Data on fetal outcome and breastfeeding are collected for regulatory reporting and drug safety evaluation. Follow-up should be conducted for each pregnancy to determine outcome, including spontaneous or voluntary termination, details of the birth, and the presence or absence of any birth defects, congenital abnormalities, or maternal and/or newborn complications, by following until the first well-baby visit. Pregnancy should be recorded on a Clinical Trial Pregnancy form and reported by the investigator to the sponsor or its designee. Pregnancy follow-up information should be recorded on the same form and should include an assessment of the possible causal relationship to the sponsor's study drug to any pregnancy outcome, as well as follow-up to the first well-baby visit or the duration specified in local regulations, whichever is later. Refer to the Incyte Reference Guide for Completing the Clinical Trial Pregnancy Form.

Any SAE occurring during pregnancy must be recorded on the SAE report form and submitted to the sponsor or designee.

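### Scheduled pregnancy testing ends at Week 12 although extension dosing has no fixed maximum, and the pregnancy reporting rule does not clearly cover the 93 days after last dose

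*Protocol*

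**What the plan says.** **Testing.** Protocol 8.3.5.6 requires a serum test at screening for women of childbearing potential and then says: "Urine pregnancy tests will be conducted as outlined in Table 1, as medically indicated, or per country-specific requirement". In Table 1 the urine row is marked at Day 1 and at Weeks 1, 2, 4, 6, 8, 10 and 12, and is blank at Months 1, 2 and 3. Table 2 governs the extension and its follow-up and has no pregnancy row. Section 8.1 gives the default for the extension: "Unless noted below, procedures listed in this section are not required to be performed in the extension period of the study". Section 8.3.5.6 has no extension paragraph, whereas 8.1.5, 8.3 and 8.3.5 each have one. SAP 8.3.2 also refers pregnancy testing to the schedule of assessments.

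**Dosing and withdrawal.** Under Protocol 4.1, extension dosing continues "until the drug is available through another clinical study, or is commercially available, or the sponsor stops the study or the study drug development". The first mandatory reason for stopping study drug in 7.1.1 is "The participant becomes pregnant".

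**Avoidance and reporting.** Inclusion criteria 7b (women) and 7c (men) require pregnancy avoidance "from screening through at least 93 days after the last dose of study drug". Section 9.4 opens its required steps with "When a pregnancy has been confirmed in a participant during maternal or paternal exposure to study drug". Those steps are to stop study drug at once and to send the pregnancy form within 24 hours; follow-up of the outcome comes in the next paragraph.

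**The concern.** There are two separate gaps.

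The first is detection during dosing. The plan tests at every treatment visit for 12 weeks. It then keeps the mandatory withdrawal rule but drops the scheduled test that would trigger it, during a dosing period with no stated end. Extension visits are 8 to 12 weeks apart, so a pregnancy not suspected clinically could remain exposed for some time.

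The second is collection after dosing. The protocol asks women and men to avoid pregnancy for at least 93 days after last dose, but its reporting section is keyed to exposure and does not mention those days. A site could reasonably decide that a conception at day 60 after last dose needs no form and no outcome follow-up. Pregnancy-outcome data would then be incomplete for a period in which the protocol itself asks participants to avoid pregnancy.

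**Working it through.** This is a matter of schedule and definitions. The plan states no figure to reproduce, so the check is a comparison of sections plus day counts.

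**1. Scheduled tests.** Table 1 marks Day 1 and Weeks 1, 2, 4, 6, 8, 10 and 12, which is 8 urine tests. Months 1 to 3: 0. Table 2 has 8 rows (medications, dispensing, accountability, AEs, PJP prophylaxis, hematology, hemolysis markers, serum chemistries), and none is a pregnancy test.

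**2. Days without a scheduled test.** Inputs: 12 weeks × 7 = 84 treatment days (Protocol 4.1) and 93 days after last dose (5.1). Extension length is not given, so E is an assumption.

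- Total days from Day 1 to the end of the window = 84 + E + 93
- Days after the last scheduled test = E + 93

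| Assumed extension E | Days without scheduled test | Total days | Share |
|---|---|---|---|
| 0 | 93 | 177 | 53% |
| 182 (26 weeks) | 275 | 359 | 77% |
| 365 (1 year) | 458 | 542 | 85% |
| 730 (2 years) | 823 | 907 | 91% |

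The shares describe the calendar only. They are not probabilities of a missed pregnancy.

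**3. Does the last visit reach day 93?** Assume that the EOT visit falls on the day of last dose. Section 8.9.2 describes follow-up as both 12 weeks and 3 months, and Table 1 allows ± 5 days at Month 3.

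- Month 3 = 84 days: 84 ± 5 = days 79 to 89, so 93 − 89 = 4 to 93 − 79 = 14 days short.
- Month 3 = 91 days: 91 ± 5 = days 86 to 96, so from 7 days short to 3 days past.

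**4. Is a pregnancy reportable?**

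- In the extension: the participant is still exposed, so 9.4 and 7.1.1 both apply once the pregnancy is known. The gap here is detection only.
- After last dose: 9.4 does not define exposure and does not mention 93 days, and its first step, stopping study drug, presupposes current dosing. Coverage is unclear.
- AE collection does not fill the gap. Under 9.4, pregnancy in itself is not an AE unless interference with contraception is suspected. Section 9.3.2 limits SAE reports beyond 30 days after last dose to those with suspected causality.

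**The case against.** **Testing does not stop altogether.** A reader might infer that it does. Section 8.3.5.6 keeps medically indicated and country-required tests, and a note to Table 5 allows extra tests agreed with the sponsor. This stands: only scheduled testing ends.

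**The extension text may already include the test.** The extension paragraph in 8.3.5 refers to Table 5, which lists a urine pregnancy test. But that paragraph names only hematology panels and hemolysis markers and defers to standard of care. Table 5 also contains screening-only items, so the reference cannot mean that every entry is repeated. It does not supply a schedule.

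**The lean extension schedule looks deliberate.** Table 2 also omits vital signs, ECGs and physical examinations. That is fair as a description of the design. Pregnancy, however, is the one specific medical finding on the mandatory list in 7.1.1, and the documents give no reason for ending its test while dosing continues.

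**Section 9.4 may reach beyond dosing.** Its second paragraph speaks of following each pregnancy and is not expressly limited, exposure could be read to include a period after last dose, and a sponsor reference guide is cited that is not available here. This stands in part. A reader might infer that pregnancies after last dose are excluded, but the text shows ambiguity, not exclusion.

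**The 93 days are a contraception requirement.** Section 5.1 does not call them a surveillance period, and the text available here describes no specific reproductive hazard. This also stands. The case is that two sections of one protocol should be reconciled, not that a stated surveillance period has been breached.

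**Conclusion.** Both gaps are present in the text. Scheduled testing falls from 8 tests in 12 weeks to none for the rest of participation, whatever the length of the extension, so an exposed pregnancy may be detected late. Separately, pregnancies in the 93 days after last dose are not clearly within the collection rule.

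Two stronger readings should be avoided. One is that pregnancies during the extension go uncollected; once known, they fall under 9.4. The other is that the final visit always precedes day 93; that depends on reading Month 3 as 84 days and on EOT falling on the day of last dose, and with 91 days the visit may come after day 93.

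The number of participants affected cannot be estimated. About 25 are planned, and the documents do not say how many will be women of childbearing potential or will enter the extension. No efficacy endpoint is affected, and SAP Appendix A plans no pregnancy table or listing. The consequence is for participant safety and for the completeness of pregnancy data. The change should be made because it is inexpensive and closes a mismatch within the protocol.

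**What to change.** 1. Reconcile Table 2 and 8.3.5.6 with 7.1.1. Carry Table 1's existing urine-test row, for women of childbearing potential, into the extension schedule at visits already held, and add an extension sentence to 8.3.5.6. The sponsor sets the frequency.
2. State in Tables 1 and 2 whether the test applies at EOT of the extension and in follow-up. If it does not, say so and give the reason.
3. Reconcile 9.4 with 5.1. Define the pregnancy collection period, for maternal and paternal exposure, to run through the protocol's own 93 days after last dose, and keep the instruction to stop study drug for participants still on it.
4. State whether Month 3 means 84 days or about 91 days, and how pregnancy status is obtained if the last visit falls before day 93.

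The cost is amendment wording, a site urine test at visits already scheduled, and possibly one brief contact per participant whose last visit falls before day 93.
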